## 5. STUDY DESIGN

## 5.1 Summary of Trial Design

This is a single centre, randomised, two-period, crossover study with the following experimental period sequences:

AEX intervention: prolonged sitting for ≈6 hours (h) 15 minutes (min) punctuated by 30min AEX performed at 60% VO₂peak

Control: prolonged sitting for ≈6h 45min

Group 1) Control at visit 2 and then intervention at visit 4

OR

Group 2) Intervention at visit 2 and then control at visit 4

[figure not shown]
The expected study duration is approximately one month per participant. Participants will attend six visits in total (Figure 1).

Figure 1: Study flowchart

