On day 1 for each treatment arm (Visit 1 and Visit 3) a blinded CGM device (Dexcom G6) will be fitted to participants in addition to the accelerometer they will already be wearing (visit 1 only). The CGM will be worn continuously from visit 1 to visit 5. If the period between visit 1 and visit 5 is more than 10 days (which is the recommended use for the Dexcom G6 sensor), then a second CGM sensor (Dexcom G6) will be inserted at visit 3 for the second treatment period. If the window between visit 1 and visit 5 is less than 10 days then this visit 3 can occur remotely. A brief reminder will be provided to all participants in CBG testing in case of HYPO symptoms and in HYPO treatment and we will ensure that a blood glucose meter is still available to them from the screening visit. A glucose monitoring diary to record symptoms suggestive of hypoglycaemia, glucose levels at the time that they experience these symptoms and the treatment received for hypoglycaemia will also be provided to all participants at visit 1. Additionally, participants will be asked to complete a 3-day diet diary (as described above). Finally, all participants will be provided with a standardised meal from the research team to consume on the evening before each of Visits 2 and 4 (day 2 of each treatment period), no later than 10h before their study visit. Participants will be asked to fast and refrain from any food or drink, other than water (which may be consumed ad libitum), after

consumption of this standardised meal. Participants will be allowed to consume caffeinated drinks on the day before each of visits 2 and 4, but will be asked to record and replicate these as per any other food or drink item in both treatment periods, and not drink these after consumption of their standardised meal.

In a case where the participant will not need to attend visit 3 in person, all the above aspects will be covered in the phone call or video call with a participant at a time of visit 3.

Participants will be provided with a standardised evening meal to take and consume at a set time at home, as well as with a 3-day diet diary. This could be but is not limited to providing the meals and a diary at the previous visit or delivering the meals and a diary to the participant's home.

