#### 7.8 Randomisation

Randomisation will take place at the level of the individual using an independent online computerised randomisation service (sealed-envelope.com). Eligible participants will be randomly assigned at Visit 1 in a 1:1 ratio to the following treatment sequence:

Participants will be individually randomised (1:1) using a block design to one of the two trial sequences (below);

 Prolonged sitting for ≈6h 45min (control) followed by sitting [total ≈6h 15min] and one bout of AEX for 30min

or

Sitting (total ≈6h 15min) and one bout of AEX for 30 min followed by prolonged sitting for ≈6h
 45min (control).

Randomisation outcome will be revealed by a member of the study team. The independent researchers revealing randomisation allocation will sign the delegation of authority log and follow a local SOP to reveal the randomisation as requested.

Participants will be informed of their randomisation assignment during the Visit 1.

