#### 11. STATISTICS

#### 11.1 Description of Statistical Methods

A CONSORT study flow diagram will detail the movement of participants throughout the BariEX study. Baseline descriptive characteristics will be summarised, with continuous variables expressed as mean values (and standard deviations) or median values (with lower and upper quartiles) where appropriate, and binary and categorical variables expressed as number (percentage). Where CGM data is missing from a given trial, the corresponding data will be excluded from the other trial during the same time period at the second treatment. Participants with less than 16-hours 48min CGM data available for analysis over the 24-hour period after the intervention will be excluded from the complete cases analysis. The primary outcome of the study will be the difference in the time spent in HYPO (defined as glucose levels <3.0 mmol/l as measured by CGM) between the AEX and control intervention during the first 24-h post-intervention.

For outcomes related to the standardized MMTT (secondary outcomes), data from blood samples collected pre-MMTT at lunchtime (exactly before MMTT consumption) and 15, 30, 60, 90, 120, 150 and 180 minutes after MMTT consumption (last mouthful of MMTT) will be used to calculate time-averaged AUC (Area Under the Curve), using the trapezium rule. In instances of symptomatic hypoglycaemia during the MMTT(where blood collection for glucose, insulin and appetite biomarkers as well as VAS scores for satiety and hunger will be terminated early), these participants will be excluded from the analysis of secondary outcomes related to the MMTT. Missing data on insulin, glucose, appetite biomarkers and VAS scores for satiety and hunger within a completed MMTT will be imputed using a linear regression method as previously reported (35, 36), provided baseline/pre meal value and ≥50% of data points within the MMTT are available. The primary and secondary outcomes will be analysed using GEE (Generalised Estimating Equations) with an exchangeable correlation matrix, taking into account repeated measures across conditions. Outcome distribution will be assessed, with Gamma models used for positively skewed data. Identity and log link functions will be explored with Gamma models, with an identity link preferred (to aid interpretation of results) unless log link provides a substantially superior model fit.

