The primary and main secondary outcomes will be analysed using a complete case approach. A sensitivity analysis will also be conducted where individuals in whom rescue action for symptomatic hypoglycaemia during the first 24-h post-intervention was required will be excluded from the

analysis. A second sensitivity analysis will be performed using individuals with any CGM data (i.e. including those with CGM data available for analysis is <16hours 48mins for the first 24 hours post-intervention). A value of P<0.05 will be considered statistically significant for all analyses. Statistical analyses will be carried out using commercially available statistical programmes.

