#### 11.2 The Number of Participants

This is a proof-of-concept study and there are no previous data available on the acute effect of AEX on time spent on HYPO after bariatric surgery. Previous studies have found that people without diabetes after bariatric surgery spend on average 71±25 min/day in HYPO postoperatively (37) and that the incidence may be similar between RYGB and SG (13). Based on this previous research, the current we estimate that the research project is powered (80%) to detect a 25% difference (18 minutes/day) in time spent in HYPO during the first 24-hs between the AEX and control interventions, with 2-sided alpha set at 5% and assuming a standard deviation of 25min and a moderate within-person correlation of 0.6. On this basis, 18 participants are required for this crossover study (accounting for an estimated drop-out of 20%).

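### The primary GEE for this two-period crossover names no period term; adding one costs almost nothing and protects the exercise-control contrast when completers are unequal

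*Protocol*

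**What the plan says.** Protocol section 5.1 describes the design: "This is a single centre, randomised, two-period, crossover study", with control then exercise in one sequence and exercise then control in the other. Section 7.8 adds: "Participants will be individually randomised (1:1) using a block design to one of the two trial sequences".

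Section 11.1 analyses the primary and secondary outcomes by generalised estimating equations "with an exchangeable correlation matrix, taking into account repeated measures across conditions". It sets Gamma models for positively skewed outcomes and a rule for choosing between identity and log links. It continues: "The primary and main secondary outcomes will be analysed using a complete case approach". Neither period nor sequence is mentioned anywhere in section 11.

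The washout in section 5.1 is there to remove carry-over of the exercise effect on glucose. It is not offered as a safeguard against a difference between periods. On the sensor, section 5.1 says: "The CGM will be worn continuously from visit 1 to visit 5". It adds that a second sensor is fitted at visit 3 when visit 1 to visit 5 takes more than 10 days.

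**The concern.** In a two-period crossover, period is part of the design. Anything that makes hours in period 2 differ from hours in period 1, whatever the condition, enters each participant's exercise-control difference with opposite sign in the two sequences. If period is not in the model, two things follow. With equal sequences the period effect cancels from the estimate, but it stays in the residual spread and widens the standard error. With unequal sequences it no longer cancels and moves the estimate.

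Section 5.1 presents the two treatment periods as alike except for the intervention, but the protocol itself shows ways in which they can differ. Visit 3 may be remote, whereas visit 1 is face to face. Participants have had practice with the diary, the glucose meter and self-treatment by period 2. For participants who keep one sensor throughout, that sensor is several days older in period 2. The trial plans for about 14 completers and uses complete cases, so unequal sequences are likely.

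**Working it through.** **Inputs.** From section 11.2: "powered (80%) to detect a 25% difference (18 minutes/day) in time spent in HYPO", "with 2-sided alpha set at 5% and assuming a standard deviation of 25min and a moderate within-person correlation of 0.6", and 18 participants allowing for 20% drop-out. Completers: 18 × 0.8 = 14.4, taken as 14. The period effect p (period 2 minus period 1) is not in the documents; 0, 5, 10 and 15 minutes are assumed values.

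**The plan's own figure.**
- SD of the within-person difference = 25 × √(2 × (1 − 0.6)) = 22.36 minutes.
- Normal approximation: n = ((1.96 + 0.842) × 22.36 / 18)² = 12.1, so 13; 13 / 0.8 = 16.25, so 17.
- Noncentral t: n = 15; 15 / 0.8 = 18.75, so 19; or 15 × 1.2 = 18.

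The stated 18 is reproduced within one participant.

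**Effect of leaving period out.** The expected exercise-control difference is 18 + p in the control-first sequence (n1 completers) and 18 − p in the exercise-first sequence (n2 completers). Without a period term:
- bias = p × (n1 − n2) / (n1 + n2);
- expected sample variance of the differences at 7:7 = 22.36² + p² × 14/13. For p = 10 this is 500 + 107.7 = 607.7, an SD of 24.7 minutes in place of 22.4.

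**Power at 7:7, true effect 18 minutes** (simulation; paired analysis without period, two-sequence analysis with period):

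| Period effect | Without period | With period | Type I error without period |
|---|---|---|---|
| 0 min | 79.4% | 78.9% | 5.0% |
| 5 min | 77.9% | 79.0% | 4.5% |
| 10 min | 73.4% | 79.1% | 3.3% |
| 15 min | 65.2% | 79.0% | 1.9% |

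A repeat with 400,000 runs per cell gave 77.9%, 72.9% and 65.0% without period at 5, 10 and 15 minutes. A GEE with exchangeable correlation and identity link, fitted to one simulated 7:7 data set with a 15-minute period effect, gave the same estimate with and without period (19.1 minutes). The standard error fell from 9.04 to 7.74 when period was added.

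**Bias with unequal completers, per 10 minutes of period effect.**
- 8:6: 10 × 2/14 = 1.4 minutes.
- 9:5: 10 × 4/14 = 2.9 minutes.
- With period in the model: zero in both.

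The sign depends on which sequence loses more. At p = 10, 9:5 in favour of control-first rejects in 85.6% of runs without period against 75.4% with it; the reverse split rejects in 57.7% against 75.5%.

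**How likely is imbalance?** Assume 9:9 at randomisation and four losses at random. There are 3,060 ways to choose the four.
- 7:7: 36 × 36 / 3,060 = 42%.
- 8:6 either way: 2 × 9 × 84 / 3,060 = 49%.
- 9:5 either way: 2 × 126 / 3,060 = 8%.

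So the sequences end unequal in about 58% of cases, mostly by one step.

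**Sensor age.** The period 1 window starts about one day after insertion. One sensor can serve both periods only if visit 1 to visit 5 fits in 10 days. That means a washout of about 3 to 7 days counted from visit 2 (section 5.1), or 3 to 5 days with the visit spacing in Appendix 3. The period 2 window then starts about 5 to 9 days after insertion. With longer washouts, up to 28 days, the sensor is refitted at visit 3 and its age is about one day in both periods.

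**The case against.** The strongest reply is that the point is read from silence. The words on repeated measures describe the correlation structure. Section 11.1 does not list the terms of the mean model, nor does it say that condition is the only one. Section 11.5 refers to a statistical analysis plan, which is not shown and may well name period. This stands: a reader might infer that the trial ignores period, and the protocol does not establish that. Still, section 11.1 goes into detail on estimator, correlation, distribution and link for a design it calls two-period. Naming the one further term that the design calls for belongs in the same place.

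A reader might also infer that sensor age differs between periods by design. That holds only for participants who keep one sensor over a short washout, and no passage says that sensor age shifts readings below 3.0 mmol/l in a consistent direction. The sensor is a possible source, not a demonstrated one. The same goes for familiarity with procedures: monitoring is blinded and meals are replicated.

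Finally, it is tempting to say that leaving period out removes the protection given by randomising the order. It does not. Allocation is 1:1 in blocks, and with equal completers the estimate is unbiased and the test errs on the cautious side. Nor is power always lost: with no period effect the model without period is slightly better, and with imbalance in one direction it rejects more often, because of the bias.

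**Conclusion.** The point holds as a cheap improvement to the stated analysis, conditional on a statistical analysis plan that is not shown. Its size depends wholly on a period effect that the documents do not give. At 5 minutes or less with equal completers it is about one point of power. At 10 and 15 minutes it is about 6 and 14 points. The more awkward consequence is bias with unequal completers: 1.4 minutes at 8:6 per 10 minutes of period effect, against an 18-minute target. The 9:5 figure of 2.9 minutes needs all four losses to fall in one sequence, which chance alone gives about 8% of the time. The figures assume normally distributed differences, the plan's SD and correlation, 14 completers, and a t reference distribution; the Gamma variant was not examined.

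**What to change.** State in section 11.1 that the GEE for the primary and secondary outcomes includes condition and period as fixed effects. If the statistical analysis plan already says so, a cross-reference is enough. It would also help to record the sensor day at each intervention and report it by period. No formal carry-over test is needed.

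The cost is one degree of freedom. If there is no period effect, power at 14 completers falls from 79.5% to 78.9% at 7:7. With unequal sequences the cost is larger, because the adjusted estimate weights the two sequences equally: about 1.3 points at 8:6 (79.6% to 78.3%) and about 4 points at 9:5 (79.2% to 75.2%). The t-based requirement of 15 completers does not change (82.6% to 82.1%).

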#### 11.2 The Number of Participants

This is a proof-of-concept study and there are no previous data available on the acute effect of AEX on time spent on HYPO after bariatric surgery. Previous studies have found that people without diabetes after bariatric surgery spend on average 71±25 min/day in HYPO postoperatively (37) and that the incidence may be similar between RYGB and SG (13). Based on this previous research, the current we estimate that the research project is powered (80%) to detect a 25% difference (18 minutes/day) in time spent in HYPO during the first 24-hs between the AEX and control interventions, with 2-sided alpha set at 5% and assuming a standard deviation of 25min and a moderate within-person correlation of 0.6. On this basis, 18 participants are required for this crossover study (accounting for an estimated drop-out of 20%).

#### 11.3 The Level of Statistical Significance

The results of all comparative analyses will be presented with 95% confidence intervals and statistical significance for main effects will be assessed at the 5% level. All p-values shown will be two-sided.

#### 11.4 Criteria for the Termination of the Trial.

There are no specific criteria for terminating the trial prematurely. The end of the trial is defined as when primary and secondary outcomes are all analysed.

#### 11.5 Procedures for Reporting any Deviation(s) from the Original Statistical Plan

Any deviation(s) from the original statistical analysis plan will be described and justified in the final report.

# 12. DIRECT ACCESS TO SOURCE DATA/DOCUMENTS

Direct access will be granted to authorised and delegated members of the study team, authorised representatives from the sponsor, host institution, and the regulatory authorities to permit trial-related monitoring, audits and inspections.

#### 13. QUALITY CONTROL AND QUALITY ASSURANCE PROCEDURES

The study will be conducted in accordance with the current approved protocol, ICH GCP, relevant regulations and standard operating procedures (SOPs).

The University of Leicester, as Sponsor, operates a risk based monitoring and audit program, to which this study will be subject. The Study will also be subjected to an additional COVID-19 Sponsor Risk Assessment prior to opening to make sure adequate measures are in place to ensure safety of Participants and staff.

The study team will conduct regular QC checks on study data to ensure all data that is captured is accurate for the duration of the study. The study team will also be responsible in ensuring the site files are maintained and all relevant study documents are within the site file.

All source data, study documents, and participant notes will be made available for monitoring, audits and inspections by the Ethics Committee, the Sponsor and the Regulatory Authority.

#### 14. CODES OF PRACTICE AND REGULATIONS

#### **14.1** Ethics

Participants will be free to withdraw at any time from the study without giving a reason and without their legal rights being affected. All study procedures including risks involved will be explained clearly to participants at the screening part of Visit 0 and subsequently before each procedure is performed.

The overall care and comfort of the participant will always be considered paramount during the study. The randomised crossover study design ensures random allocation to intervention sequence. The inclusion and exclusion criteria ensures patients are not included if there is a risk of damage to their health through exercise.

#### 14.2 Standard Operating Procedures

All relevant Sponsor, host organisation and study specific SOPs will be followed where applicable to ensure that this study complies with all relevant legislation and Guidelines.

#### 14.3 Declaration of Helsinki

The Investigator will ensure that this study is conducted in full conformity with the current revision of the Declaration of Helsinki (last amended October 2000, with additional footnotes added 2002 and 2004).

#### 14.4 ICH Guidelines for Good Clinical Practice

The Investigator will ensure that this study is conducted in full conformity with relevant regulations and with the ICH Guidelines for Good Clinical Practice (CPMP/ICH/135/95) July 1996.

#### 14.5 Approvals

Once Sponsor authorisation has been confirmed, all study documentation will be submitted to appropriate regulatory bodies (e.g. REC/ HRA), the sponsor and the host institution for written approval. The study will commence upon receiving Sponsor green light.

Once Sponsor authorisation has been confirmed, the Investigator will submit and, where necessary, obtain approval from the above parties for all amendments.

#### 14.6 Participant Confidentiality

The study will comply with the Data Protection Act which requires data to be anonymised as soon as it is practical to do so. Participants will be identified only by their initials and unique study ID number on the CRF and the electronic database (REDCAP). Samples will only be identified by Study ID number, visit number and time of collection. Access to the database, samples and all documents will be restricted to study staff and authorised personnel from the Sponsor, host NHS Trust and regulatory authorities. The database will be maintained and accessed via University Hospitals of Leicester networks and servers. Study data will be stored for 5 years.

All research data will be kept in a secure office environment within Leicester Diabetes Centre, Leicester General Hospital during the active phase of the study and until the data have been analysed. Consent forms will remain on site at all times during the life-cycle of the study, it will then be archived in line with University of Leicester policy unless consent has been given for the samples to be used for future ethically approved research. In such instances, the consent form will be retained for evidence of the provenance of the sample and the consent from may be transferred to another organisation/individual where material transfer agreements are in place. The consent form will be retained by the custodian of the sample(s) at all times. Where consent has been given, identifiable data will be retained on a volunteer's database for future research.

#### 15. DATA HANDLING AND RECORD KEEPING

All study documentation will be managed in accordance with ICH-GCP, the UK Policy Framework for Health and Social Care Research (2017), General Data Protection Regulation (2018) and the Data Protection Act (2018).

Participants will be allocated a unique study ID number which will be used on all hard and electronic copies research documentation, data, and blood samples collected from the point of consent onwards.

The Case Report Forms (CRFs) and research database (REDCAP) will identify participants by their Study ID number, and samples will contain the Study number in addition to the visit number and time of collection. As such, all source data and samples will be pseudonymised and access will be limited to the delegated members of the research team (including those conducting analysis of samples working at Loughborough University). Access to the source data, database and Trial Master File will also be granted to delegated individuals from the Sponsor (University of Leicester), the host NHS organisation (University Hospitals of Leicester NHS Trust) and regulatory authorities for monitoring and auditing purposes.

Database containing identifiable information for the purpose of contacting participants will be held on the host NHS organisation (University Hospitals of Leicester NHS Trust) servers, and access will be limited to delegated members of the research team only. The Study database (REDCAP) is password protected and is owned and maintained by the host NHS organisation (University Hospitals of Leicester NHS Trust). Final data analysis will be conducted on servers owned and maintained by the host NHS organisation (University Hospitals of Leicester NHS Trust) and /or the Sponsor (University of Leicester) and/or those delegated the task of sample analysis (Loughborough University).

The Trial Master file and CRFs will be retained in a secure location within the Leicester Diabetes Centre and will then be archived for 5 Years following the end of study in line with the Sponsor SOP.

Eleven glucose blood samples (11 per visit, 22 in total) per patient will be sent for analysis in UHL laboratories following visits 2 and 4, these results will be sent to the research team to be entered in the CRF. The 11 glucose samples taken for the study will be destroyed once analysed in accordance with the UHL's SOP's. Further to this, insulin and biochemical markers of appetite will be stored as

plasma samples and will be kept until analysed, if consent is obtained (for the biochemical markers of appetite) and if feasible (for the biochemical markers of appetite).

If participants consent for their samples to be stored for future research then plasma will be collected into monovettes for analysis. Blood samples will be centrifuged at the point of collection with the plasma stored in microtubes in a -80 degree freezer. As these bloods are not being stored as whole blood, they do not require HTA licensed laboratory storage. These plasma samples will be stored in a research laboratory at Leicester General Hospital for future ethically approved research. We are unable to specify a period of time for storage of the plasma samples for measurement of appetite biomarkers.

